#### Visit 16 (Month 36 ± 28 days)

Visit 16 will include:

- Clinical assessment of neoplasia in the selected treatment area (biopsy if there is suspicion of SCC, BCC or other neoplasia)
- Dermatologic examination of selected treatment area including AK count
- Reporting of (S)AEs (see [Table 3](#))
- Reporting of concomitant medication, treatments and procedures
- Abbreviated physical examination

[figure not shown]
#### Unscheduled/Early Termination

Upon completion of the last visit or during the study, an unscheduled visit may be required for any subject with a severe reaction, suspected pregnancy or an unresolved treatment-related AE or LSR, if deemed clinically significant by the investigator. Only assessments that require follow-up will be conducted if the subject is continuing in the trial. For early termination, all trial assessments scheduled should be performed if possible.

### 10.1.4 Study Design Diagram

Figure 1 Study Design

### 10.2 TIME SCHEDULE

Planned date of first subject first visit: Q2 2013

Planned date of last subject first visit: Q2 2015

Planned date of completion of last subject: Q2 2018

### 10.3 NUMBER OF SUBJECTS/SAMPLE SIZE

A total of 480 subjects will be enrolled in the trial and randomised 1:1 to the two treatment groups. With 240 patients in each treatment group an adequate precision of the 3-year incidence rate can be obtained. Assuming a 3-year rate of 1.0%, the upper 95% confidence limit

---

will on average be 2.26%, and assuming a 2.5% rate, the upper 95% confidence limit will on average be 4.48%.

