### **Enrolled Subject**

A subject for whom informed consent has been obtained and a CRF number assigned.

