### 8.3 TRIAL RATIONALE

The purpose of this trial is to evaluate the risk of SCC after the treatment with ingenol mebutate gel. Imiquimod has been chosen for comparison as the treatment that is most comparable marketed field treatment with regard to efficacy. The cumulative incidence of SCC in a cohort of subjects with multiple AKs on the face or scalp who have been treated with ingenol mebutate gel or imiquimod cream will be evaluated.

To ensure accurate diagnosis a biopsy of a representative lesion will be taken to confirm AK prior to randomisation. Further, the biopsy is expected to identify a number of subjects who have SCC at screening and are therefore not eligible for the trial. In order to increase the likelihood of detecting an increased risk, if any, the subjects in both groups will be treated for 2 cycles if complete clearance is not obtained at Week 8. To obtain a reasonable number of SCC cases, subjects will be followed for 3 years and will be assessed for SCC (and other neoplasias) in the treatment area at regular intervals.

The overall design will be a two-arm trial where patients are initially all treated with one cycle of either ingenol mebutate gel or imiquimod cream according to the normal treatment schedule for face and scalp. Subjects in the imiquimod group will be treated according to the approved EU dosage regimen. After 8 weeks, patients who are completely cleared of all AKs in the selected treatment area will continue further observation in the Follow-up period, whereas those who are not cleared will be retreated with a second treatment cycle. For the purpose of this trial the minimum period between the two treatment cycles, i.e. the period between the initial treatment cycle and possible retreatment, will be 8 weeks which is the time

---

when the treatment response would be evaluated in clinical practice for both products. Adverse events, LSRs and efficacy will also be compared between the two treatments.

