### **10.5 WITHDRAWAL CRITERIA**

The investigator is free to withdraw the subject at any time for medical reasons.

Subjects **may** withdraw for any of the following reasons:

1. *Unacceptable adverse events or LSRs*: any adverse event or LSR that the investigator or the subject considers unacceptable.
2. *Exclusion criteria*: any exclusion criteria which emerge/become apparent during the subject's participation in the clinical trial.
3. *Voluntary withdrawal*: subjects will be free to withdraw from the clinical trial at any time and for any reason.
4. *Other reasons*: other reasons than stated above which requires the subject to (be) withdraw(n) should be specified.

Subjects, who are discovered, after randomisation, not to have fulfilled all in-/exclusion criteria at time of enrolment, should be withdrawn from treatment unless the investigator, based on clinical and ethical evaluation, finds withdrawal from treatment inappropriate. If a biopsy is taken for suspicion of neoplasia in the treatment area, the subject should likewise be withdrawn from treatment.

Such deviation(s) from the (Consolidated) Clinical Study Protocol must be reported to LEO Pharma A/S (and the IEC/IRB, as appropriate) and recorded in the Clinical Study Report.

Subjects who withdraw from the trial should be asked to complete the early termination visit.

Reason(s) for withdrawal will be recorded in the CRF.

Subjects withdrawn after randomisation will not be substituted.

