## **10.15 COMPLETION OF TRIAL**

### **10.15.1 Trial Completion Procedures**

The end of trial is the date of the last subject's last visit.

Investigators will be informed when subject recruitment is to cease.

Trial enrolment will be stopped at a trial site when the total requested number of subjects for the clinical trial has been obtained, irrespective of the specific site's planned inclusion number.

Upon completion of the clinical trial, LEO Pharma A/S will undertake arrangements for collection and disposal of any unused trial material that the investigator is not required to keep in his/her files.

LEO Pharma A/S may stop the clinical trial prematurely after consultation with the international co-ordinating investigator, e.g. if the subject recruitment is so slow that the clinical trial cannot be completed within a reasonable time frame. Notification of such premature termination/suspension of the trial will be given to regulatory authorities and IECs/IRBs, as required.

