7.3.1 Censoring

Since the primary and secondary safety criteria are time-to-event analyses, a censoring scheme will be defined. This is not detailed in the CCTP.

Subjects from the safety analysis set will be included in the time-to-event analyses, as described in [Table 1](#):

Table 1: Censoring

Event	Date	Outcome
SCC	Date of biopsy	Event
Missing result from a biopsy	Date of biopsy	Censored
Trial completion without SCC	Date of last visit with assessment and no SCC	Censored
Trial discontinuation	Date of last visit with assessment and no SCC	Censored
Death from any cause	Date of death	Censored

SCC: Squamous cell carcinoma

In addition, a PP censoring will be defined, which is censoring at the time when a subject is excluded from the PP analysis set, as described in [Table 2](#):

Table 2: PP censoring

Event	Date	Outcome
Exclusion from PP analysis set with no documented SCC	Date of last visit with assessment before exclusion with no SCC	Censored

PP: Per protocol, SCC: Squamous cell carcinoma

Details on censored subjects are given by subject ID in the analysis set definition document.

Trial ID: LP0041-63	Date: 28-AUG-2019	Version: Final 1.0 Page 10 of 32
---------------------	--------------------------	-------------------------------------

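### The upper limits that justify the sample size in 10.3 assume every subject is followed for 36 months; with no drop-out allowance they are modestly too low under the formula that produced them

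*Protocol*

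**What the plan says.** Protocol 10.3 sets the size of the trial: "A total of 480 subjects will be enrolled in the trial and randomised 1:1 to the two treatment groups". The justification is "With 240 patients in each treatment group an adequate precision of the 3-year incidence rate can be obtained". The first case reads "Assuming a 3-year rate of 1.0%, the upper 95% confidence limit" and puts that limit at 2.26% on average. The second takes a rate of 2.5% and puts the limit at 4.48%. The synopsis repeats both. No drop-out rate or inflation factor appears in either place.

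Elsewhere the plan allows for incomplete follow-up. Protocol 10.5 lets subjects leave at any time and adds "Subjects withdrawn after randomisation will not be substituted". Protocol 10.10.6.1 calls for survival methods suited to censored data. SAP 7.3.1, Table 1, censors a subject who discontinues at "Date of last visit with assessment and no SCC", and also censors deaths and biopsies without a result. SAP 7.3.2 estimates cumulative incidence as one minus the Kaplan-Meier curve.

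On wording, Protocol 4.2 defines an enrolled subject as "A subject for whom informed consent has been obtained and a CRF number assigned". The CRF number is assigned at Visit 1 (10.4.4), before the screening histology is known. Section 8.3 says that "the biopsy is expected to identify a number of subjects who have SCC at screening and are therefore not eligible for the trial".

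**The concern.** The precision of each arm's 3-year SCC rate is the only reason given for 240 per arm, because 10.10.6.1 plans no formal comparison. Over 36 months some subjects will leave, and the plan expects this. A precision figure that ignores it describes a better-informed analysis than the one that will be run. Readers of the report could then compare the achieved intervals with limits that the design supports only if nobody leaves. The trial is a post-approval commitment to the regulator (8.2.1), so the precision claim should match the planned analysis.

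**Working it through.** **Inputs from the documents.** n = 240 per arm; p = 1.0% or 2.5%; stated limits 2.26% and 4.48% (Protocol 10.3). Withdrawals are not replaced (10.5). Kaplan-Meier with censoring (SAP 7.3.1, 7.3.2).

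**Assumptions.** The documents give no drop-out rate, so d = 10%, 20% and 30% by Month 36 is a range chosen here. Event and drop-out hazards are taken as constant and independent.

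**Step 1: reproduce the stated limits.** Formula: p + 1.96 × √(p(1 − p)/n).

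- p = 1.0%: 0.010 + 1.96 × √(0.010 × 0.990/240) = 0.010 + 1.96 × 0.006423 = 2.259%
- p = 2.5%: 0.025 + 1.96 × √(0.025 × 0.975/240) = 0.025 + 1.96 × 0.010078 = 4.475%

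Both match. The formula counts all 240 as observed to Month 36.

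**Step 2: same normal form, with censoring.** Let L = −ln(1 − p) and M = −ln(1 − d). The large-sample Greenwood variance of the 3-year Kaplan-Meier estimate is

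V = (1 − p)²/n × I, with I = [L/(L + M)] × [1/((1 − p)(1 − d)) − 1].

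With d = 0 this reduces to p(1 − p)/n, as in Step 1.

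Example, p = 1.0% and d = 20%: L = 0.01005, M = 0.22314, so I = 0.04310 × 0.26263 = 0.01132. Then V = 0.9801 × 0.01132/240, SE = 0.006799, and the limit is 0.010 + 1.96 × 0.006799 = 2.333%.

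| Drop-out d | Limit at p = 1.0% | Limit at p = 2.5% | Effective n, p(1 − p)/V |
|---|---|---|---|
| 0 (as stated) | 2.26% | 4.48% | 240 |
| 10% | 2.29% | 4.53% | about 228 |
| 20% | 2.33% | 4.59% | about 214 |
| 30% | 2.38% | 4.67% | about 200 |

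The rise over 10% to 30% drop-out is 0.03 to 0.12 percentage points at the 1.0% rate and 0.05 to 0.19 points at the 2.5% rate.

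**Step 3: does this hold for other limits?** Section 10.3 describes its limits as averages, but the formula in Step 1 is the limit at the assumed rate, not an average.

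- Averaged over the binomial distribution, the two-sided Wald limit at n = 240 with no loss is 2.16% and 4.43%.
- Simulated with Kaplan-Meier censoring, the average Wald limit at the 1.0% rate is about 2.24% even at 30% drop-out, still below 2.26%. At the 2.5% rate it passes 4.48% somewhere between 10% and 20% drop-out.
- Average Wilson limits at n = 240 with no loss are 3.20% and 5.31%. Average Clopper-Pearson limits are 3.19% and 5.33%.

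**The case against.** The strongest reply is that the effect is small and nothing turns on it. The limits are illustrative, are not success thresholds, and feed no test. The analysis is built for censoring, so early leavers contribute up to their last assessment: at 20% drop-out the effective size is about 214, not the 192 who complete. The choice of interval method also matters far more. Clopper-Pearson limits average about 3.2% and 5.3% before anyone leaves. All of this stands, and it bounds the size of the point. It does not remove the point, because the one stated justification still omits a loss that the plan itself provides for.

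Three stronger readings are tempting, and the documents do not support them.

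- A reader might infer from the 4.2 definition, the expected biopsy failures and the stopping rule ("Trial enrolment will be stopped at a trial site when the total requested number of subjects for the clinical trial has been obtained") that fewer than 240 per arm will be randomised. But 10.3 says the 480 are randomised 1:1 and puts 240 in each treatment group, and subjects who fail screening are in no treatment group. Section 10.15.1 does not say that its total counts consented subjects. Only a mismatch of terms is left.
- A reader might infer that the stated limits are too low under any interval method. Step 3 contradicts this for the average Wald limit. A one-sided Wald limit with 192 subjects is also lower than both stated figures, at 2.18% and 4.35%.
- A reader might infer that the stated limits are bound to be exceeded in the report. For the average Wald limit, that depends on the true rate and the amount of drop-out.

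**Conclusion.** The point holds in a limited form. The limits 2.26% and 4.48% are two-sided Wald limits at the assumed rates for 240 per arm with complete 36-month follow-up. For that formula, any loss raises them: to between 2.29% and 2.38%, and between 4.53% and 4.67%, for 10% to 30% drop-out. The direction follows from the plan's own censoring and non-replacement rules. The size rests on assumed drop-out rates, constant hazards and censoring that is independent of SCC risk. The sample-size statement is modestly optimistic. The number randomised is not in doubt, and the planned estimate is not invalid.

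**What to change.** Keep 240 randomised per arm. In 10.3 and the synopsis, declare a drop-out assumption, or a range such as 10% to 30%, and restate the expected upper limits for it. Compute them with the Kaplan-Meier interval that will be reported, and name that interval: SAP 7.3.2 gives the normal form for the difference between arms but not the interval type for each arm. This matters because restating with the Wald form alone would leave the larger effect of the interval method untouched.

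As a minor wording change, write *randomised* for *enrolled* where the target number is meant: 10.3, the synopsis, the per-site figure in 10.10.5 and the stopping rule in 10.15.1.

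The cost is a few lines of text and slightly less favourable stated limits. The number randomised and the trial procedures do not change.

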**Number of subjects entered:**

A total of 480 subjects will be enrolled in the trial and randomised in a 1:1 ratio to the two treatment groups. With 240 patients in each treatment group an adequate precision of the 3-year incidence rate can be obtained. Assuming a 3-year rate of 1.0%, the upper 95% confidence limit will on average be 2.26%, and assuming a 2.5% rate, the upper 95% confidence limit will on average be 4.48%,

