## 10.10.6 Safety Analysis

### 10.10.6.1 Analysis of Primary and Secondary Safety Endpoints

The primary endpoint and secondary safety endpoint are listed in sections [10.9.1](#) and [10.9.2](#) respectively. Both endpoints will follow the same method of analysis.

The 3-year cumulative incidence will be calculated for each treatment group using methods of survival analysis for estimation of cumulative incidence in the presence of censored time-to-event data. Annual incidence rates will also be presented for each group. The cumulative incidence rates will be presented for the event of SCC as primary endpoint and for SCC and other neoplasia as secondary. No formal statistical test comparing the two arms will be performed. For descriptive purposes, as an additional analysis, the difference in cumulative incidence rates between the two arms will be estimated and presented together with its 95% confidence interval.

A landmark analysis, conditional on patients' responses at Week 20, will additionally be performed in order to exclude SCC and other neoplasia reported within the first 20 weeks which are not assumed to be associated with the study treatment. Patients who experience a neoplasia before the 20-week landmark time point are excluded from the time-to-event analysis, which is otherwise conducted as above.

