7.3.2 Primary Safety Criterion

The primary safety criterion is diagnosis of SCC (defined as invasive SCC, i.e. excluding SCC in situ) in the treatment field across the 3-year trial period. Invasive SCC is diagnosed by biopsy.

The CCTP states: “*The 3-year cumulative incidence will be calculated for each treatment group using methods of survival analysis for estimation of cumulative incidence in the presence of censored time-to-event data. Annual incidence rates will also be presented for each group. The cumulative incidence rates will be presented for the event of SCC as primary endpoint and for SCC and other neoplasia as secondary. No formal statistical test comparing the two arms will be performed. For descriptive purposes, as an additional analysis, the difference in cumulative incidence rates between the two arms will be estimated and presented together with its 95% confidence interval.*”

The time to first SCC in months will be calculated as days divided by the average number of days in a month:

$$(\text{Date of biopsy} - \text{date of first exposure to trial medication})/30.4375$$

The cumulative incidence rate with 95% confidence intervals (CIs) will be estimated for each treatment group using SAS *PROC LIFETEST* where the *STRATA* statement will include the randomisation stratification factors *country, anatomical location, and history of SCC*, and with the option *GROUP=treatment*. The incidence rates will be presented using the option *TIMELIST=12 24 36* for 1, 2 and 3 years, respectively. Cumulative incidence will be presented by 1 minus the survival curves estimated using the Kaplan-Meier method. Moreover, numbers at risk and censoring information will be presented by treatment group.

The analysis will be presented for the safety analysis set. In addition, the analysis will be presented for the PP analysis set using PP censoring as described in section 7.3.1. Please see the analysis set definition document for details.

The additional analysis of difference in the 3-year cumulative incidence rates will be calculated as the difference between the Kaplan-Meier estimates of each treatment group and will be presented with 95% CI. The difference is assumed to be approximately normally distributed, and as the treatment groups are assumed to be independent and identically distributed, the 95% CI will be calculated as $\pm 1.96 \times \sqrt{(SE_{Ing}^2 + SE_{Imi}^2)}$ where SE_{Ing} and

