7.5.3 Handling of Drop-outs and Missing Values

Drop-outs will be handled as described in section 7.3.1 for the primary and secondary safety criteria using censoring in time-to-event analyses.

Missing results from biopsies will be handled using censoring as described in section 7.3.1.

Besides this, no imputation will be implemented.

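### The average upper 95% limits in protocol 10.3 (2.26% and 4.48%) are Wald limits at the assumed rate, and overstate precision by about 0.6 to 1.2 percentage points

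*Protocol*

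**What the plan says.** Protocol 10.3 plans 480 subjects, randomised 1:1, and rests the size on one claim: "With 240 patients in each treatment group an adequate precision of the 3-year incidence rate can be obtained". The support is two figures. At an assumed 3-year rate of 1.0%, the upper 95% limit "will on average be 2.26%, and assuming a 2.5% rate, the upper 95% confidence limit will on average be 4.48" per cent. The synopsis repeats them ("Assuming a 3-year rate of 1.0%, the upper 95% confidence limit will on average be 2.26%, and assuming a 2.5% rate"). Neither place names an interval method, a sidedness or a drop-out allowance.

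There is no power calculation behind the number, because protocol 10.10.6.1 states: "No formal statistical test comparing the two arms will be performed". The difference between arms is descriptive.

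For the analysis, SAP 7.3.2 says: "The cumulative incidence rate with 95% confidence intervals (CIs) will be estimated for each treatment group using SAS" PROC LIFETEST, and: "Cumulative incidence will be presented by 1 minus the survival curves estimated using the Kaplan-Meier method". It does not name the interval for the single-arm estimates. It does give a normal-approximation interval for the difference, ±1.96 times the root of the summed squared standard errors. Shells 5, 6 and 9 require upper limits. No rule covers an arm with no SCC.

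**The concern.** The two limits are the only quantitative support for the claim of adequate precision. A Wald interval is unreliable when only 2.4 or 6 events are expected in an arm. Its error here is on the optimistic side, understating the SCC risk that the trial cannot exclude. Protocol 8.2.1 describes the trial as a post-approval commitment to the EMA, so readers are likely to rely on the precision statement.

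A smaller, related matter sits in the SAP. If an arm has no SCC, its Kaplan-Meier standard error is 0 and a log-log limit is undefined, so the plan leaves open what the upper-limit cell will show.

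**Working it through.** **Inputs.** n = 240 per arm; assumed rates 1.0% and 2.5%; confidence level 95% (all protocol 10.3). Two-sided, z = 1.96, from the general rule in 10.10, because 10.3 gives no sidedness. Complete 3-year follow-up is assumed throughout unless stated.

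**1. Reproducing the plan's figures.** U = p + 1.96·√(p(1−p)/240).

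- p = 0.010: √(0.010 × 0.990/240) = 0.006423; U = 0.010 + 1.96 × 0.006423 = 2.259%.
- p = 0.025: √(0.025 × 0.975/240) = 0.010078; U = 0.025 + 1.96 × 0.010078 = 4.475%.

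These round to 2.26% and 4.48%. Other candidates do not give both figures: one-sided Wald 2.06% / 4.16%; two-sided Wald with continuity correction 2.47% / 4.68%, one-sided 2.26% / 4.37%; Poisson Wald 2.27% / 4.50%; and, at the expected count, Wilson 3.24% / 5.35%, Clopper-Pearson 3.23% / 5.36%, Jeffreys 2.91% / 5.08%. That the method is Wald is therefore an inference from the match.

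**2. What the average is.** With X ~ Binomial(240, p), the average upper limit is Σ P(X = x)·U(x). For Wald this gives 2.16% and 4.43%. The stated figures put the assumed rate into the formula; they are not averages over outcomes.

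**3. Wald coverage.** Exact two-sided coverage is 90.7% at 1.0% and 93.2% at 2.5%. The Wald upper limit is 0 at x = 0, 1.23% at x = 1, 1.98% at x = 2 and 2.66% at x = 3.

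- At a true rate of 1.0% it falls below the truth only at x = 0: 0.99^240 = 9.0%.
- At 2.5% it falls below at x = 0, 1 or 2, together 6.0%.
- The nominal figure is 2.5%.

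**4. Alternatives**, by the same enumeration. Without censoring, S = 1 − x/n and the log-log upper limit is 1 − S^exp(1.96·θ), where θ = √((1−S)/(nS))/|ln S|. An exact binomial limit is used at x = 0.

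| Interval | Average upper limit, 1.0% / 2.5% | Two-sided coverage |
|---|---|---|
| Stated in 10.3 | 2.26% / 4.48% | (Wald) 90.7% / 93.2% |
| Jeffreys | 2.85% / 5.04% | 96.5% / 96.5% |
| Clopper-Pearson | 3.19% / 5.32% | 98.9% / 96.5% |
| Log-log Kaplan-Meier | 3.48% / 5.47% | 96.5% / 95.7% |

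**5. Size of the gap.** Jeffreys: 2.85 − 2.26 = 0.59 and 5.04 − 4.48 = 0.56 points. Log-log: 3.48 − 2.26 = 1.22 and 5.47 − 4.48 = 0.99 points. The range is about 0.6 to 1.2 points.

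**6. Censoring (assumption only).** The documents give no drop-out rate. In a simulation of 60,000 arms with 10% or 20% leaving evenly over 36 months, the log-log limit averages 3.61% or 3.75% at a 1.0% rate, and 5.58% or 5.71% at 2.5%. The simulation does not model the visit window.

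**7. An arm with no SCC.** The chance is 0.99^240 = 9.0% at a 1.0% rate and 0.975^240 = 0.2% at 2.5%. The exact upper limit for 0/240 is 1 − 0.025^(1/240) = 1.53%. The denominator matters. The Month 36 visit has a ±28-day window (protocol 3.1.2), completers are censored at their last visit (SAP 7.3.1), and the estimate is read at exactly 36 months (SAP 7.3.2). A completer seen early is then no longer at risk. If visits were spread evenly over the window (an assumption), about 120 of 240 would remain at risk without any drop-out, and the limit would be 1 − 0.025^(1/120) = 3.0%. That doubling would reflect scheduling, not lost information.

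**The case against.** The strongest reply is that nothing turns on these figures. No target limit is set, the comparison is descriptive, and the reported intervals come from SAP 7.3.2, not from 10.3. Normal-approximation planning figures are common shorthand. The SAP is dated 28 August 2019, after the planned completion in Q2 2018 (protocol 10.2), so rewording 10.3 changes neither enrolment nor results. This stands as a limit on the weight of the point. It does not make the figures right: they are presented as averages and 95% limits, they are neither reliably, and the claim of adequate precision has no other support.

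Three stronger readings are tempting, and the documents support none of them.

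- *The trial is too small.* About 525 per arm (at 1.0%) or 420 (at 2.5%) would bring the average Clopper-Pearson limit down to the stated values. But the protocol never says that those values are required.
- *The SAP will report an upper limit of 0.* It does not say so; it is silent on the zero-event case. If 0 were shown, log-log coverage at a 1.0% rate would fall to 87.5%, but that is a possibility to close off, not a stated plan.
- *The unnamed Kaplan-Meier interval is itself an error.* It is missing detail. SAP 7.5.3 deals with drop-outs ("Drop-outs will be handled as described in section 7.3.1 for the primary and secondary safety criteria using censoring in time-to-event analyses"), and SAP 7.3.2 adds: "Moreover, numbers at risk and censoring information will be presented by treatment group".

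**Conclusion.** The precision statement in 10.3 and the synopsis is wrong as written. It understates the average upper limit by about 0.6 to 1.2 points, depending on the interval: about 2.8–3.5% at a 1.0% rate and 5.0–5.5% at 2.5%, against 2.26% and 4.48%. These figures assume 240 per arm with complete 3-year follow-up; censoring widens the limits further. No threshold is breached, and 240 per arm is not shown to be the wrong size. The zero-event gap in the SAP is secondary. It matters mainly if the true rate is near 1.0% or lower.

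**What to change.** **Match the planning figures to the reported interval.** In SAP 7.3.2, name the interval, for example log-log limits with the Greenwood standard error. In 10.3 and the synopsis, replace the sentence with:

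> With 240 patients per arm and complete 3-year follow-up, the upper two-sided 95% limit will on average be about 3.5% if the true 3-year rate is 1.0% and 5.5% if it is 2.5%; censoring will widen it.

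If Clopper-Pearson figures (3.2% and 5.3%) are quoted instead, say that they are a planning approximation and that the reported Kaplan-Meier limits will be somewhat wider. Otherwise 10.3 would again promise more than the analysis delivers.

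**Add a zero-event rule to SAP 7.3.2.** For an arm with no SCC, report an exact binomial upper limit, not 0 or a blank. Use as denominator the subjects assessed at the Month 36 visit within its window, not the number at risk at exactly 36.0 months, and state it (1.53% for 0/240). In the same case, do not use the ±1.96 × SE interval for the difference, because that arm contributes a standard error of 0. Use a score-type interval such as Miettinen-Nurminen or Newcombe on the same denominators.

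**Cost.** Wording in 10.3, the synopsis and SAP 7.3.2, and a less favourable precision statement. No patients are added, and no endpoint or trial conduct changes.
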